6.12.5. Hospitalizations and Blood Transfusions

Hospitalizations and blood transfusions will be collected during the study treatment period and during the 30-day post discontinuation follow-up period (Visit 801).

The number of subjects requiring hospitalization, the number of hospitalizations per subject, and duration of hospital stay for each event and for each subject will be summarized by treatment group using descriptive statistics. Any patients with a hospitalization admission and discharge date on the same day are counted as a half-day in the duration of hospitalization. End dates will be imputed as the data cutoff date for patients with hospitalization ongoing at the time of analysis.

A listing of all patients who were hospitalized will be provided. The listing will include the reason for hospitalization (that is, AE, protocol test, or other), MedDRA PT, start and end dates, and duration of hospitalization.

The number of prior, concomitant, and post-discontinuation blood transfusions and transfused units per subject will be summarized by the type of blood product transfused (that is, packed red blood cells, whole blood, platelets, fresh frozen plasma, or other).

Additionally, patients that received prior, concomitant, and post-discontinuation transfusions will be listed. The listing will include the date of transfusion, type of blood products received, number of units transfused, and MedDRA PT for each patient.

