In the East Asia (China, Taiwan, and South Korea) ASIAN-Pacific trial, which compared sorafenib with placebo in patients with advanced liver cancer with no prior systemic treatment, median OS was 6.5 months (95% CI: 5.56, 7.56) in patients treated with sorafenib, compared with 4.2 months (95% CI: 3.75, 5.46) in those who received placebo (HR: 0.68 [0.50–0.93];  $p=.014$ ). Median TTP was 2.8 months (95% CI: 2.63, 3.58) in the sorafenib group compared with 1.4 months (95% CI: 1.35–1.55) in the placebo group (HR: 0.57 [0.42–0.79];  $p=.0005$ ). The most frequently reported grade 3/4 drug-related adverse events (AEs) in the 149 assessable patients treated with sorafenib were hand-foot skin reaction (16 patients [10.7%]), diarrhea (9 patients [6.0%]), and fatigue (5 patients [3.4%]) (Cheng et al. 2009).

Given these results, sorafenib is the first-line standard of care for patients with advanced liver cancer who are not candidates for surgical or local treatment. However, if the treatment with

sorafenib failed, there is no approved second-line therapy. Available results of sorafenib in the Asian population are summarized in [Table JBAS.5.1](#).

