### Antitumor Activity of LY2157299 in First-Line Patients

Preliminary results from 20 sorafenib-naïve patients (3 of whom had received brivanib as a first-line treatment and 17 who had not received any systemic treatment) who were considered ineligible to receive sorafenib were treated with LY2157299 monotherapy. These patients had an estimated median TTP of 18.3 weeks, higher than TTP in second-line HCC patients. Such patients who are ineligible to receive sorafenib generally have a reduced prognosis than do patients who are physically fit to receive sorafenib. Together with the preclinical information, this justifies the evaluation of the combination in first-line HCC.

It is anticipated that LY2157299 will increase immunocompetence in HCC patients and show increased antitumor activity due to a reduction in fibrogenesis, remodeling, neoangiogenesis, and invasiveness.

The proposed immunomodulatory as well as anti-invasive properties of LY2157299 suggest that a clinical investigation in the first-line setting of patients with HCC is promising. Hence, it may be acceptable to treat patients with LY2157299 even before they are considered to receive sorafenib or other antivascular agents.

In summary, the combination of a well-tolerated agent such as LY2157299 in a disease with high unmet medical need, justifies the evaluation of this agent in the first-line treatment of HCC. Thus, the overall benefit/risk profile is acceptable in this setting.

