4.3. Exploratory Objectives

- to explore markers associated with EMT transformation and the TGF- β -associated signaling pathway presence in the original diagnostic tumor tissue and optional posttreatment tumor tissue and the correlation of this with both clinical efficacy endpoints and biomarker response
- to explore TTP, PFS, and ORR by immune response RECIST (irRECIST)
- to explore tumor volume changes of measurable lesions on computed tomography/magnetic resonance imagings (CT/MRIs) obtained for tumor response as an assessment of treatment effects on biological growth rate
- to explore the relative effects of LY2157299 versus LY2157299 plus sorafenib versus sorafenib plus placebo on antiangiogenesis as assessed by dynamic contrast-enhanced MRI (DCE-MRI) metrics and on tumor cellularity/cell death as assessed by diffusion-weighted MRI (DW-MRI) metrics. These exploratory MRI techniques will

only be performed at clinical sites where the associated MRI center scanner has been qualified prior to patient enrollment by the imaging core laboratory designated by the sponsor.

- to explore fibrosis-related tests, such as fibrotest
- to assess healthcare resource utilization including transfusions and hospitalizations.

5. Study Design

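### Hospitalizations, hospital days and transfusions are summarized as per-subject totals over a window set by time on treatment, with no person-time denominator, so arms are not comparable if treatment duration or early mortality differs

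*SAP*

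**What the plan says.** SAP 6.12.5 fixes the collection window: hospitalizations and transfusions "will be collected during the study treatment period and during the 30-day post discontinuation follow-up period". Protocol 10.2.2 and 12.2.11 use the same window. SAP Table JBAS.6.1 defines the study treatment period as running from treatment start to discontinuation, and SAP 5.1 lets treatment continue until a discontinuation criterion is met. The window therefore has no common length.

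For hospitalizations, the section reports the number of subjects hospitalized, and "the number of hospitalizations per subject, and duration of hospital stay for each event and for each subject will be summarized by treatment group". For transfusions, the number of prior, concomitant and post-discontinuation "blood transfusions and transfused units per subject will be summarized by the type of blood product transfused". Protocol 12.2.11 makes both summaries by treatment group. The hospitalization output is "summarized by treatment group using descriptive statistics"; no test or model is planned.

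The section sits within the safety analyses and also serves the exploratory objective "to assess healthcare resource utilization including transfusions and hospitalizations". Exposure and the number of patients completing each cycle are summarized elsewhere (Protocol 12.2.11, SAP 6.12.1.3), but neither document uses them as a denominator for these events.

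**The concern.** A per-subject total over an open-ended window mixes two things: how often the event happens, and how long the patient is watched. Here the second depends on treatment, because observation stops 30 days after discontinuation, or earlier at death. Two arms with the same admission rate will show different totals if their patients stay on treatment for different times.

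What is at stake is how the columns are read side by side. Protocol 8.2 gives the safety comparison with sorafenib as the purpose of the monotherapy arm, and says that the three-arm layout should help to differentiate safety profiles and inform Phase 3. A reader who compares admissions or transfused units per patient across arms could take a difference in follow-up for a difference in burden. The total is also not a patient's overall resource use, because care after the 30-day visit is not collected.

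**Working it through.** The documents give no expected figure for hospitalizations or transfusions, so there is nothing of the plan's own to reproduce. The check is an illustration of how far totals can move when rates are equal.

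**Inputs.**
- Sorafenib TTP in the East Asian trial (Protocol 5): "Median TTP was 2.8 months (95% CI: 2.63, 3.58) in the sorafenib group". At 4.348 weeks per month this is 12.17 weeks.
- Sorafenib median TTP in the US/EU trial (Protocol 5): 5.5 months, or 23.9 weeks.
- LY2157299 in 20 sorafenib-naive patients (Protocol 5.2): "These patients had an estimated median TTP of 18.3 weeks, higher than TTP in second-line HCC patients". Protocol 5.1.5.1 gives a 90% CI from 6.3 weeks to nonestimable.
- LY2157299 300 mg/day arm of Study JBAK, mostly sorafenib-pretreated (Protocol 5.1.5.1): 10.9 weeks.
- Assumptions not in the documents: TTP stands in for time on treatment, time on treatment is exponential, and event rates are constant and equal in both arms.

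**Formula.** Mean window = median / ln 2 + 30/7 weeks. Expected total per subject = rate × mean window. At equal rates the ratio of totals is the ratio of windows, and the rate cancels.

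**Windows.**
- Sorafenib: 12.17/0.693 + 4.29 = 21.8 weeks, or 23.9/0.693 + 4.29 = 38.8 weeks.
- Monotherapy: 18.3/0.693 + 4.29 = 30.7 weeks; 10.9/0.693 + 4.29 = 20.0 weeks; 6.3/0.693 + 4.29 = 13.4 weeks.

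**Monotherapy against sorafenib** (ratios from unrounded windows):

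| Monotherapy median | Sorafenib median | Windows (weeks) | Ratio of totals |
|---|---|---|---|
| 18.3 weeks | 2.8 months | 30.7 / 21.8 | 1.40 |
| 10.9 weeks | 2.8 months | 20.0 / 21.8 | 0.92 |
| 18.3 weeks | 5.5 months | 30.7 / 38.8 | 0.79 |
| 6.3 weeks (lower CI limit) | 2.8 months | 13.4 / 21.8 | 0.61 |

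These pairings are illustrations, not bounds. Crossing 10.9 weeks with 5.5 months gives 20.0/38.8 = 0.52.

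**Combination against control.** The documents give no discontinuation hazard ratio, so one is assumed. With a control mean time on treatment of 17.56 weeks:
- HR 0.8: (17.56/0.8 + 4.29)/21.84 = 1.20.
- HR 0.667, the design value for OS, borrowed here: (17.56/0.667 + 4.29)/21.84 = 1.40.

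**Subjects ever hospitalized.** This measure moves less. At an assumed 0.1 admissions per patient-month, with mean time on treatment m in months and a 30-day tail of 0.986 months, the expected proportion is 1 − exp(−0.1 × 0.986)/(1 + 0.1m). With m = 4.04 for control and 4.04/0.667 = 6.06 for the combination, this gives 35.5% and 43.6%, a ratio of 1.23. Mean admissions are 0.50 and 0.70 per subject.

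**Early deaths.** Let discontinuation have hazard h = ln 2/2.8 per month in both arms, let death have hazard d throughout, and let L = 0.986 months. Mean window = 1/(h + d) + [h/(h + d)] × [1 − exp(−dL)]/d.
- d from 0.03 to 0.06: 4.47 to 4.02 months, ratio 0.90.
- d from 0.03 to 0.10: 4.47 to 3.55 months, ratio 0.79.
- d from 0.05 to 0.15: 4.16 to 3.09 months, ratio 0.74.

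The death hazards are assumed. The totals fall by these factors only if admission rates are unrelated to approaching death.

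With a person-time denominator every ratio above is 1.00. That follows from setting the rates equal and constant; it does not show that a rate removes all bias.

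**The case against.** The strongest reply is that this is a descriptive summary with no test or decision rule, mainly for an exploratory objective, in arms of 30, 60 and 30 patients. Exposure, patients completing each cycle, and deaths on therapy and within 30 days (SAP 6.12.4) are all reported. The listings give admission and transfusion dates. A careful reader could see unequal exposure and approximate a rate. This stands, and it limits the seriousness. But an approximation from separate tables does not handle the 30-day tail, death and hospital days patient by patient, and the SAP does not plan one.

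A reader might infer that the longer-treated arm will show about 40% more events. The documents do not support that as a prediction. Patients may continue past objective progression or stop for toxicity (Protocol 7.3.1, 10.1), so TTP is not time on treatment. The 18.3 weeks comes from 20 patients considered ineligible for sorafenib, in a study population that was 92% non-Asian, and it is set against an East Asian sorafenib trial. Other figures in the same documents reverse the direction.

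A reader might also infer that an arm with more early deaths must look better. That fails if admissions and transfusions cluster before death.

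Finally, SAP 6.12.5 does not say that protocol-test admissions will be separated in the summary. The listing records the reason for each admission, so they can be identified, and nothing in the documents suggests how many there will be. That alone is not a defect of weight.

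**Conclusion.** The point holds as a limit on interpretation. The planned totals confound event rate with length of observation whenever treatment duration or early mortality differs between arms, and neither document corrects for this. Hospitalization counts, total hospital days, the number of subjects hospitalized and on-study transfusions are affected. Stay per event and prior transfusions are not.

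Size and direction cannot be fixed in advance. The tabulated window ratios for monotherapy to sorafenib run from about 0.6 to 1.4, and the assumed discontinuation HRs of 0.8 to 0.667 give 1.2 to 1.4 for the combination. All rest on exponential time on treatment, equal constant event rates, and either TTP as a stand-in or an assumed HR.

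It would be too strong to conclude that a formal comparison is biased or that the trial's main result is at risk. No such comparison is planned, and the primary OS analysis does not use these data.

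**What to change.** In SAP 6.12.5, add a descriptive table by arm of admissions, hospital days and on-study transfused units per patient-month at risk. Define time at risk from first dose to the earliest of death, 30 days after discontinuation, or data cutoff. Keep the per-subject counts alongside.

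No new data are needed. SAP Table JBAS.6.5 already derives actual days on study to treatment discontinuation, and admission, transfusion and death information is already planned for the listings. Modelled rate ratios and a separate row for protocol-test admissions are optional.

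The cost is one derived variable and one table. A single rate averages over risk that changes during treatment. It also does not fully remove informative discontinuation, since patients with many events may leave early, so the table should say so.

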### 10.2.2. Resource Utilization

Investigators will be asked to document the use of best supportive care measures, concomitant medications, transfusions, and treatment-related hospitalization days. Such assessments are to be taken throughout the study through the 30-day safety follow-up visit.

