### 10.3. Safety Evaluations

Investigators will be responsible for monitoring the safety of patients who have entered this study and for alerting Lilly or its designee to any event that seems unusual, even if this event may be considered an unanticipated benefit to the patient.

The investigator will be responsible for the appropriate medical care of patients during the study.

The investigator will remain responsible for following, through an appropriate healthcare option, AEs that are serious, that are considered related to the study, or that caused the patient to discontinue before completing the study. The patient should be followed until the event is resolved or explained. Frequency of follow-up evaluation is left to the discretion of the investigator.

The timing of all safety evaluations is shown in the Study Schedule ([Attachment 1](#)).

[Table JBAS.10.2](#) describes AE and SAE collection with regard to the type of events to be reported during each period of the study.

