### **12.2.11. Safety Analyses**

All safety summaries and analyses will be based upon the Safety Population as defined in Section [12.2.1](#).

Overall exposure to study drug, the numbers of patients completing each cycle, and the dose intensity will be summarized using descriptive statistics. The number of patients with any dose adjustment will be presented for entire treatment period as well as for each cycle. The number of patients with dose reductions, dose delays, or dose omissions will also be summarized, as will the reasons for dose adjustments.

An overall summary of AEs will be provided for AEs deemed by the investigator to be possibly related to study medication and will be repeated for events regardless of study drug causality. Incidence rates of these events will be compared between treatment arms using Fisher's exact test.

Safety analyses will include, but are not limited to, the following:

- all reported AEs, including seriousness, severity, and possible relationship to study drug, using CTCAE terminology and grades
- TEAEs, including seriousness, severity, and possible relationship to study drug, using CTCAE terminology and grades
- dose adjustments for any study therapy
- physical examination and other safety observations, including those specifically targeting the monitoring of cardiac safety
- laboratory measures

AE terms and severity grades will be assigned by the investigator using CTCAE version 4.0. MedDRA version 16 (or higher) will be used when reporting AEs by MedDRA terms. The MedDRA lower level term will be used in the treatment-emergent computation. A TEAE, defined as an event that first occurred or worsened in severity after baseline, will be summarized by SOC and by decreasing frequency of preferred term within SOC.

Laboratory and nonlaboratory CTCAEs will be summarized by CTCAE term and maximum CTCAE grade, including the total for maximum Grades 3 and 4. These summaries will be provided for events regardless of study drug causality and will be repeated for events deemed by the investigator to be possibly related to study medication.

Reasons for death will be summarized separately for on-therapy and within 30 days of last dose of study drug. SAEs will be summarized by preferred term.

Hospitalizations and transfusions during the study treatment period or during the 30-day safety follow-up period will be summarized by treatment group.

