The simulations indicate that, by randomizing 120 patients, the posterior probability of concluding superiority of the combination arm over the control arm is approximately 83% (strong prior) and 74% (weak prior) ([Table JBAS.5.2](#)). Assuming an HR of 1, the posterior probability of concluding superiority of the combination arm over the control arm (that is, type I error) is approximately 14% to 15%. For comparison purpose, a frequentist analysis using the log-rank test would give a power of 73% assuming the HR = 0.667 and type I error = 14% (one-sided).

Table JBAS.5.2. Simulation Results for Final Analysis

N (Deaths)	Control Rate Prior	Timing of Analysis	Type I Error	Posterior Probability (HR <1) > 0.84
120 (100)	Strong prior for final analysis	FPV + 32.7 months	14%	83%
120 (100)	Weak prior for final analysis	FPV + 32.7 months	15%	74%

Abbreviations: FPV = first patient visit; HR = hazard ratio.

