Screen failures	Patients who have signed informed consent, do not meet eligibility criteria and are not treated/randomized.
Randomized	Patients who have been assigned to study treatment but may have not received any study treatment (LY2157299, LY2157299-matched placebo, or sorafenib).
Patients on therapy	Patients who have been randomized to study treatment and have received at least 1 dose of study treatment (LY2157299, LY2157299-matched placebo, or sorafenib).
Study day	If assessment is on or after date of first treatment dose then (date of assessment) – (date of first study treatment dose) + 1 If assessment precedes first treatment dose then (date of assessment) – (date of first study treatment dose) There is no study day 0. Study day 1 is the date of first dose and study day -1 is the day before the first dose.
Cycle day	If assessment is on or after date of first treatment dose then (date of assessment) – (date of first study treatment dose in cycle) + 1 If assessment precedes first treatment dose then (date of assessment) – (date of first study treatment dose in cycle) There is no cycle day 0. Cycle day 1 is the date of first dose in the cycle and cycle day -1 is the day before the first dose.
Baseline	For change from baseline analysis, baseline value is defined as the last reported measure on or before the first dose date (or discontinuation, if no treatment is given). For change from baseline within a cycle, the measure prior to the first dose if that cycle is baseline.
Study treatment period	Time from treatment start to discontinuation from study treatment
Post-discontinuation – short-term follow-up	The short term follow-up period begins 1 day after discontinuation of study treatment and lasts approximately 30 days (Visit 801).
Post-discontinuation – long-term follow-up	The long-term follow-up period begins 1 day after the short-term follow-up period (Visit 801) is completed and continues until death to collect survival data.

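### The hospital-stay end-date rule in SAP 6.12.5 has no cap at the close of the Visit 801 collection window or at death, so a stay left open at Visit 801 could be run to the data cutoff

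*SAP*

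**What the plan says.** Three places give the same collection period for hospitalizations:

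- SAP 6.12.5: "Hospitalizations and blood transfusions will be collected during the study treatment period and during the 30-day post discontinuation follow-up period (Visit 801").
- Protocol 10.2.2, on resource utilization: "Such assessments are to be taken throughout the study through the 30-day safety follow-up visit".
- Protocol 12.2.11, on what is reported: "Hospitalizations and transfusions during the study treatment period or during the 30-day safety follow-up period will be summarized by treatment group".

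SAP 6.12.5 then states that "duration of hospital stay for each event and for each subject will be summarized by treatment group using descriptive statistics", and gives one rule for stays without an end: "End dates will be imputed as the data cutoff date for patients with hospitalization ongoing at the time of analysis". It does not define how a stay is judged to be ongoing once collection has stopped, and it sets no limit at the close of the window, at death or at last contact. SAP 6.3 on missing data covers only time-to-event, health-outcome and PK/pharmacodynamic analyses, so nothing else in the SAP deals with a missing discharge date.

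After Visit 801 the stated purpose of follow-up is survival: "The long-term follow-up period begins 1 day after the short-term follow-up period (Visit 801) is completed and continues until death to collect survival data".

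**The concern.** The collection window and the imputation date do not match. For a patient still on treatment, or still within the 30 days, at the cutoff, the cutoff is a sensible end date. For a patient whose window closed long before, an open record says only that the patient was in hospital when collection stopped. Extending that stay to the cutoff counts days that nobody observed and that lie outside the period the protocol says is summarised.

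Duration of stay is reported by arm, and use of healthcare resources, including hospitalizations, is an exploratory objective (Protocol 6.3, SAP 4.3). Two arms have 30 patients each, so a single artefact of many months could dominate an arm's mean.

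**Working it through.** **1. The planned cutoff.** The SAP's simulation table puts the final analysis at "FPV + 32.7 months", where FPV is the first patient visit. To check this, take the SAP 5.2 inputs: control hazard h = 0.0216 per week; HR 0.667 for the combination and 1 for monotherapy; accrual of 1.7 patients per week, so A = 120/1.7 = 70.6 weeks. With uniform accrual and exponential survival, expected deaths at week t are

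n × [1 − (exp(−h(t − A)) − exp(−ht)) / (hA)].

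At 32.7 months, t = 32.7 × 4.348 = 142.2 weeks:

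- control plus monotherapy (n = 60, h = 0.0216): 60 × [1 − (0.2130 − 0.0464)/1.525] ≈ 53.4
- combination (n = 60, h = 0.0216 × 0.667 = 0.0144): 60 × [1 − (0.3565 − 0.1289)/1.017] ≈ 46.6

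The total is 100.0 deaths, so the 32.7 months is reproduced. (SAP 5.2 also gives accrual as 10 per month, which does not agree with 1.7 per week. The tabulated timing follows the weekly rate. Both accrual rates are used in step 2.)

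**2. How far the cutoff lies beyond Visit 801.** The documents give no time on treatment, so this part rests on assumptions. Time on treatment was taken as exponential with median 2.8 or 5.5 months, the two sorafenib median times to progression quoted in Protocol section 5. Survival was taken as exponential with median 8.2 months (the weighted historical figure) in all patients, independent of time on treatment. Entry was uniform over 12 months (10 per month) or 16.2 months (1.7 per week), and the cutoff was fixed at 32.7 months. The window closes 30 days after treatment ends. Among 400,000 simulated patients per scenario, restricted to those alive when a window closed before the cutoff:

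| Accrual (months) | Median time on treatment (months) | Median gap, window close to cutoff (days) | Dead before cutoff | Median days from death to cutoff, among the dead |
|---|---|---|---|---|
| 12 | 2.8 | 696 | 84% | 479 |
| 12 | 5.5 | 657 | 81% | 444 |
| 16.2 | 2.8 | 628 | 80% | 421 |
| 16.2 | 5.5 | 587 | 77% | 391 |

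The median gap runs from 587/30.44 = 19.3 months to 696/30.44 = 22.9 months.

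**3. Effect of one record.** Assume admission on day 25 of the 30-day window and no recorded discharge. Within the window the stay is 6 days (days 25 to 30). If the window closes at study month m, imputing to the cutoff adds (32.7 − m) × 30.44 days:

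| Window closes (month) | Days added | Imputed stay (days) | Added to mean, n = 30 | Added to mean, n = 60 |
|---|---|---|---|---|
| 6 | 813 | 819 | 27.1 | 13.5 |
| 12 | 630 | 636 | 21.0 | 10.5 |
| 18 | 447 | 453 | 14.9 | 7.5 |
| 24 | 265 | 271 | 8.8 | 4.4 |

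These are means per randomized patient. A mean over hospitalized patients only would move further: with 10 hospitalized (an assumed number) and closure at month 12, by 630/10 = 63 days.

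**4. What cannot be computed.** The documents give no rate of hospital stays open when the window closes. The steps above size one record, not how often such records arise.

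**The case against.** A reader might infer that the SAP ends every open hospitalization at the cutoff, and so knowingly credits days after death. The text does not say that. The rule applies to a patient whose stay is continuing when the analysis is done; a patient known to be dead or discharged is not in that group. Death dates are collected for overall survival and deaths are listed under SAP 6.12.4. Credit past death arises only if a blank end date is programmed as ongoing, which the SAP neither directs nor prevents.

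Nor does an open record have to stay open. Inpatient hospitalization is a criterion for a serious adverse event, follow-up information on such events must be notified (Protocol 10.3.1.1), and for serious events Protocol 10.3 says: "The patient should be followed until the event is resolved or explained". Some discharge dates will be obtained that way. The cutoff rule also has a proper use for patients still under collection at an interim or final cutoff. The summary is descriptive, it includes the median, and start date, end date and duration are listed for each hospitalized patient, so an extreme value would be visible.

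All of this stands, and it limits the point without removing it. Protocol 10.3.1.1 says serious events due to progression should not be reported unless possibly related to study drug, and SAP 6.12.5 allows reasons for admission other than adverse events. Resolution of an event is also not a discharge date. If ongoing is read narrowly, as confirmed still in hospital, the SAP has no rule at all for a stay left open at Visit 801.

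**Conclusion.** The rule and the collection window do not fit together, and the SAP should say what happens to a stay with no recorded discharge after Visit 801. If the present rule is applied to such a stay, the error is many months: typically about 19 to 23 months from window close to cutoff under the assumed treatment durations. One record would shift the mean of a 30-patient arm by about 9 to 27 days if the window closes between months 24 and 6. Most such patients would be expected to have died before the cutoff (77% to 84% under the same assumptions), so a blank treated as ongoing would often run past death. That last step depends on programming and is not an instruction in the SAP.

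The frequency is unknown and may be low. The mean and maximum of duration of stay are exposed and the median less so. The number of patients hospitalized, the number of hospitalizations, overall survival, the posterior-probability criterion and the interim futility threshold are unaffected.

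**What to change.** In SAP 6.12.5, replace the imputation sentence with a rule to this effect: recorded discharge dates are used as recorded; for a hospitalization with no recorded discharge date, the end date is imputed as the earliest of date of death, end of the 30-day safety follow-up period (Visit 801) and data cutoff date; imputed stays are flagged in the listing. For a patient still on treatment or within the 30 days at the cutoff, and alive, this gives the same result as now. Because the rule turns on whether a discharge date is recorded, it no longer needs a definition of ongoing.

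The cost is a short change of SAP text, one programming line and a flag in an existing listing. The downside is that a stay which truly continued past Visit 801 with no recorded discharge is cut off at the end of the window. That understates the stay, but it matches the period the protocol says is summarised, and the flag lets a reader see which stays are affected.
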